3.2 Primary Study Outcomes

The primary study outcomes include circulating metabolites that will be measured using an untargeted mass spectrometry-based platform with fasting concentrations of up to 1500 endogenous metabolites related to mitochondrial function, fatty acid oxidation, insulin resistance, and glucose regulation. Targeted metabolomics analysis for acylcarnitines and amino acids will be completed; non-targeted analyses will also be performed as an exploratory analysis, in order to promote the identification of unknown metabolites in addition to the known biology and physiology. Responses will be collected prior to, immediately post, and 1 hr post exercise.

3.2a. Secondary Study Outcomes

Counterregulatory hormones (cortisol, lactate, glucagon) will be evaluated at the same time points. Glucose will be continuously monitored for 48 h post exercise. , and glycemic control through 48 hrs after HIIT, compared to MICT versus a no exercise CON.

3.2b. Tertiary Study Outcomes

Tertiary outcomes will evaluate the influence of biological sex and physiological outcomes (i.e. body composition, lean mass, visceral fat) on the metabolomics profile of these subjects.

3.3 Subject Recruitment and Screening

Fourteen patients (7 females, 7 males) with T1D, for at least one year, will be enrolled for this study. Subjects will be primarily recruited from the UNC Endocrinology and Diabetes clinic and UNC Student Health Center. Posters and brochures will be made available in the waiting areas and exam rooms of the diabetes clinics. Additionally, eligible patients will be invited to participate in this study by mailing them an introductory letter that describes the study. These letters will be followed up with telephone calls to answer questions and encourage participation. Individuals interested in the study will be screened for eligibility criteria via a telephone screen to review a health/medical history questionnaire and physical activity readiness questionnaire (PAR-Q+). Patient history will be obtained from self-report from the participant and from available medical records specific to the participant's diabetes history, current diabetes management, other past, and current medical problems. The most recent HbA1c will be recorded (taken within the previous 3 months). Those who meet eligibility criteria and are interested in participating will meet a study team member to complete informed consent, inclusion criteria, and familiarization of the study protocol. Additionally, physician approval will be requested, either from study physician ([name], [name], or personal physician).

3.4 Inclusion Criteria

- Clinical diagnosis of presumed autoimmune T1D, receiving daily insulin
- Last hemoglobin A1c <9%
- 18-51 years
- Duration of T1D: \geq 1 year
- Body mass index (BMI) $<30 \text{ kg/m}^2$
- Generally healthy, with no conditions that could influence the outcome of the trial, and in the judgement of the investigators is a good candidate for the study, based on a review of health history

3.5 Exclusion Criteria

- Physician diagnosis of active diabetic retinopathy that could be worsened by exercise
- Physician diagnosis of peripheral neuropathy with insensate feet
- Physician diagnosis of autonomic neuropathy
- Medications: beta-blockers, agents that affect hepatic glucose production such as beta adrenergic agonists, xanthine derivatives; any hypoglycemic agent other than insulin.
- Severe hypoglycemic event defined as the individual requiring a third party of hospitalization in the last 6 months
- Diabetic ketoacidosis in the last 6 months

- Has a closed-loop pump and not willing to use manual mode
- Physician diagnosis of cardiovascular disease that would affect exercise tolerance
- Currently doing HIIT
- Severely impaired hearing or speech
- Pregnancy

3.6 Early Withdrawal of Subjects

A participant may be withdrawn from the study if they withdraw their consent, if they violate the stipulations of the study inclusion and exclusion criteria, if they are unable to comply with study pre-visit guidelines, or if consistent glucose excursions (more than 4 times) occur that do not align with requirements of the study (blood glucose <70 mL/dL; >300 mg/dL).

3.7 Method for Assigning Subjects to Treatment Regimens

During the second visit to the laboratory, participants will be randomized into exercise order. Exercise order will be randomly assigned by the PI using random allocation software. The allocation sequence will be generated with equal treatment sequence order.

4 Study Procedures

4.1 Procedures:

Pre-screening: Phone screening (~45 minutes)

Prior to the enrollment visit, each subject will be sent an electronic version of the informed consent to review the details of participation. Those interested will complete a phone screening for inclusion/exclusion criteria. If the subject qualifies for the study and is interested in participating, verbal consent will be obtained. Following verbal consent, an electronic link for written consent and for a self-reported medical health history questionnaire will be sent, respectively. Patient history will be obtained from self-report from the participant. Each subject will provide electronic written informed consent and complete the health/medical history questionnaire and a physical activity readiness questionnaire (PAR-Q+). Following written electronic consent, health history will be reviewed by the study team; approval for participation will be obtained from the subject's personal physician/endocrinologist or by the study physician.

Visit 1- Baseline Testing: (~45 minutes)

Subjects will be asked to arrive to the laboratory after an overnight fast (8 hr) and their usual dose of insulin administered the day prior, with no morning mealtime insulin the day of testing to control for the influence of food intake on metabolic rate, body composition measures, and metabolic markers. Height and weight will be recorded to obtain body mass index.

Body composition: (~15 minutes) (previously approved in IRB#17-0952, #17-0950, #16-1991, and #16-1397 with no adverse events):

A four compartment (4C) model, as previously validated by our laboratory will be used to estimate fat mass (FM; kg), percent body fat (%fat), and lean mass (LM; kg). Components of this equation include: 1) body volume, derived from a dual-energy x-ray absorptiometry total body scan (DXA); 2) total body water, measured using multi-frequency bioelectrical impedance spectroscopy (BIS); and 3) total body bone mineral density, calculated using total body bone mineral content, measured from the DXA.

- a. Dual-energy X-ray Absorptiometry (GE Lunar iDXA, GE Medical Systems Ultrasound & Primary Care Diagnostics, Madison, WI, USA) 10-15 min: A trained DXA technician will perform all scans. The subject will be asked to remove all metal, thick clothing, and heavy plastic which could interfere with the DXA scans. The subjects alphanumerical number, age, ethnicity, height and weight will be entered into the computer prior to the scanning. The subject will be asked to lie down on the DXA table in the supine position. The participant will be centered on the table within the scanning area. The subject's shoulders and hips will be centered, and the hands will be placed by the side of the legs in a prone position. (The DXA methodology planned for use has previously been approved with no adverse events: IRB#18-1025, #18-0648, #17-0950, #16-1960, #16-1397, #15-0543).

- b. Bioelectrical Impedance Spectroscopy (InBody570, BioSpace, Seoul, South Korea), subjects will be asked to stand on and grasp hold of metal electrodes. While the subject remains standing, a harmless and unperceivable electrical current is then conducted through the body. Both machines are widely-used commercial devices that are FDA approved and pose no risks. Internal to the device, the BIS utilizes 256 frequencies to estimate TBW. The TBW estimate will then be used to estimate Ms using the equation from Wang et al: $Ms = TBW \times 0.0129$. (previously approved in IRB#13-1664, #17-0952, #17-0950, #16-1991, #16-1397, #16-0529, #15-0543 with no adverse events).

Cardiorespiratory fitness (VO_2 peak): (~20 minutes)

Peak oxygen consumption (VO_2 peak; $L \cdot min^{-1}$ and $ml \cdot kg^{-1} \cdot min^{-1}$) will be used to set an appropriate individualized training load for the start of the HIIT protocol. During this ramp-based cycle ergometer test, respiratory gases will be analyzed over 15 second intervals using indirect calorimetry (Parvo Medics TrueMax 2400®, Salt Lake City, UT) until subjects reach volitional fatigue. The three highest oxygen consumption values will be averaged and recorded as the VO_2 peak. Ventilatory threshold (VT) will be determined as the intersection point of two linear regression lines fitted to the upper and lower portion of the ventilation versus VO_2 curve using manufacturer software (True One 2400® Metabolic Measurement System, Parvo-Medics Inc., Provo UT). Heart rate (HR) will be monitored throughout the test (Polar Electro Inc., Lake Success, NY), with the highest HR achieved during the test recorded as the HR_{max} . Interval intensity for the HIIT intervention will be calculated and set at 90% of the maximum wattage achieved. Intensity for the MICT intervention will be calculated and set at 65% of the maximum wattage achieved. Protocol was previously approved in IRB#16-2996, #16-0829, #14-2824, #14-0062 with no adverse events.

Familiarization and Randomization: (~10 minutes)

Subjects will be familiarized with the cycle ergometer for the HIIT and MICT exercise. For familiarization, participants will practice a few intervals and cycle a few minutes at the individualized intensity for each respective exercise. They will also be asked, and provided with instructions, to practice one session (HIIT or MICT) on their own, under a usual fed state, prior to their visit to the lab. Each practice session will occur with CGM and Garmin physical activity monitoring (described below). The sessions should mimic those of the actual exercise session; 5-10 bouts of HIIT will be recommended; MICT time frame will be based on specific calculations (described below), approximately 15-25 min. This is included to provide the research team insight into potential glucose excursions prior to the lab-based exercise session in a fasted state. Our laboratory team has successfully implemented a similar 'home-based' HIIT intervention in healthy and clinical populations, with no adverse events [IRB: 18-2393 (Endometrial Cancer); 16-0829 (Knee osteoarthritis); 15-1150 (Bone marrow transplant patients); 14-2398 (Anterior Cruciate Ligament Reconstructive patients); 13-3515 (patients with cardiovascular disease risk factors)].

Visit 3-5: Randomized Treatment Regimen: (~90 minutes to 120 minutes)

At baseline testing, subjects will be randomized to one of three treatment regimens: 1) HIIT; 2) MICT; 3) CON (no exercise). Subjects will repeat the following procedures for visits 3-5, except there will be no exercise session on the CON treatment session. Exercise sessions will occur in the Applied Physiology Laboratory on the UNC campus. **There will be a minimum of seven days between each exercise trial.**

Continuous Glucose Monitoring (CGM):

Participants will be given the option to monitor their interstitial glucose levels via their own CGM or through a Freestyle Libre Pro (Abbot Laboratories), which will be provided to them. In the case that they decide to use their own CGM, the researchers will request data only for the dates the participant is involved in the study. If a participant decided to use the Freestyle Libre Pro, sensor will be inserted subcutaneously 7 days before exercise for a period of up to 7 days post exercise. CGM metrics including percent time-in-range (TIR), percent time in hypoglycemia, and percent time in hyperglycemia will be evaluated during and 48 hrs post exercise.

Dietary Controls:

Participants will be asked to complete a diet log on the three days, with at least one day occurring the 24 hrs prior to the conditions (HIIT, MICT, CON) to obtain data on usual total caloric intake (kcals), grams of carbohydrate (CHO), protein (PRO), and fat (FAT). Participants will be asked to consume a similar meal the evening prior to each exercise session.

In addition to the diet logs, to evaluate the influence of dietary intake on glucose excursions, participants' dietary intake will also be obtained for the 24 hrs after each exercise session via 24-hour dietary recall obtained via interview by trained interviewers utilizing the Nutrient Data System for Research (NDSR) software and the multiple pass interviewing method to ensure the capture of food intake, which can impact glucose regulation. Dietary information will be used to anticipate and reduce the risk of hypo/hyperglycemic events. If necessary, it will be used as a statistical covariate during analysis.

Saliva Collection (females only) (~5 minutes): Estrogen concentrations will be determined using a 2.5 mL saliva sample taken at baseline. Estrogen levels will be determined using an ELISA assay for salivary estrogen. To determine if estradiol needs to be included as a covariate in the statistical procedures, it will be measured at baseline. Participants will be asked to avoid brushing their teeth for 45 minutes prior and undergoing dental work for 48 hours prior to sample collection to avoid blood contamination. Immediately upon arrival and prior to sample collection, subjects will be asked to rinse their mouth with water to remove any residues. All samples will be immediately frozen at -20°C until analysis using established enzymatic assays.

Physical Activity:

Daily levels of physical activity will be measured via a Garmin Vivosmart 4 fitness tracker 7 days before exercise for a period of up to 7 days post exercise. The Garmin Vivosmart 4 fitness tracker utilizes a built in Garmin Elevate™ Heart Rate monitor, altimeter, accelerometer, and Bluetooth® Smart and ANT+® technology to measure heart rate (HR), step count, floors climbed, and minutes of moderate-vigorous physical activity (MVPA). The wearable device automatically syncs to the GarminConnect application. This data will be used as a potential covariate when collating CGM data and to help understand any glucose excursions that occur.

Metabolomics (~15 minutes):

Approximately 8 mL of blood sample (~ 1.5 teaspoons) using an EDTA tube will be taken upon arrival, immediately after exercise, and one-hour post exercise. CON intervention visit will consist of a single blood draw. Circulating metabolites will be measured using an untargeted mass spectrometry-based platform with fasting concentrations of up to 1500 endogenous metabolites related to mitochondrial function, fatty acid oxidation, insulin resistance, and glucose regulation. Analysis will be completed at the Duke Molecular and Physiology Institute Metabolomics Core, directed by [name]. Targeted metabolomics analysis for acylcarnitines and amino acids will be completed; non-targeted analyses will also be performed, in order to promote the identification of unknown metabolites in addition to the known biology and physiology. Counterregulatory hormones (cortisol, lactate, glucagon) and insulin will be analyzed. Samples will be centrifuged immediately upon collection, and aliquots of plasma will be immediately frozen at -80° C for batch analysis. All blood draws will be done in the Applied Physiology Lab by an individual trained in phlebotomy. The current lab group has previously received approval for intravenous blood draws from the antecubital region in several IRB#, to name a few: 16-1991, 15-0543, and 14-0777, with no adverse events reported.

Treatment Regimens: (~20- 30 minutes)

- 1) HIIT Intervention: A 2 minute self-selected warm-up, followed by 10 alternating sets of one minute of pedaling at a resistance corresponding to 90% of VO₂peak and one-minute in active recovery at 50 watts (W). The work completed during each interval will be calculated by multiplying the power output for each participant at 90% VO₂peak by the duration of the interval (60 s). The work completed during each recovery period will be added by multiplying the power output (50 W) by the duration of the recovery period (60 s). The work from both bouts will be added together and then multiplied by 10 to calculate the total amount of work that each participant will complete in the HIIT trial.
- 2) MICT Intervention: Subjects will cycle continuously at a workload corresponding to 65% VO₂peak (W) for a pre-calculated length of time (~20-30 minutes), equivalent to the work that will be completed in the HIIT trials.
- 3) CON Intervention: No exercise will be performed. Subjects will arrive to the lab following the same pre-testing guidelines followed for HIIT and MICT trials.

HIIT and MICT interventions will be matched for energy expenditure. Heart rate and finger stick capillary glucose will be tracked throughout the duration of the exercise interventions. Indirect calorimetry will be used to evaluate caloric expenditure (kcals) and fuel utilization (respiratory exchange ratio) at the first and last three minutes of exercise. Using the same set-up and device as described for the VO₂peak, indirect calorimetry (Parvo Medics TrueMax 2400®, Salt Lake City, UT) will be used to identify carbon dioxide expiration.

4.2 Training on Procedural Intervention: All procedures performed in the present study will be overseen by the PI ([name]), as well as have formalized training and on ground oversight by experts in the area of T1 diabetes. This will include, [name], [name], [name], [name], [name], and [name]. Members of the research team will undergo training to be prepared to handle situations in which glucose excursions occur before, during, and after the exercise protocol.

5 Statistical Plan

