3.1 General Design

In a randomized controlled cross-over design, fourteen adults (7 females, 7 males) with T1D of at least 1-year duration and HbA1c $<9\%$ will undergo three conditions, in a randomized order: 1) high intensity interval training exercise session (HIIT) at 90% peak oxygen consumption (VO_2 peak); 2) moderate intensity exercise session (MICT; 65% VO_2 peak; or 3) a control session (CON; no exercise) (Figure 2).

Subjects will be asked to arrive to the laboratory after an overnight fast (8 hrs) and their usual dose of insulin administered the day prior, with no morning mealtime insulin the day of testing. The lower and higher limit for pre-exercise (i.e. fasted) glucose concentration (i.e. 10 minutes prior to the exercise start time) will be set at 90 and 250 mg/dL, respectively, and the session will be rescheduled if the pre-exercise glucose value is not in range or if hypoglycemia (blood glucose: <70 mg/dL) occurs within an hour of exercise start time. Subjects will also be asked to arrive to testing sessions following a 12 hour fast from caffeine and alcohol and to abstain from physical activity for 24 hours prior to testing. Subjects will complete one electronic contact (phone/email screening) and up to five in-person sessions (enrollment; baseline testing; three conditions [HIIT, MICT, CON]) over the course of 4 weeks

All data collection will be conducted by the Principal Investigator and Research Assistants. All subjects will report to the Applied Physiology Laboratory in [name] for consenting, enrollment, testing, and exercise sessions.

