5.1 Sample Size Determination

The proposed study was powered based on consideration of multiple effect size calculations from a single bout of HIIT vs MICT in young men ($F=0.25-0.99$)(16) on markers of carbohydrate oxidation, glucose, citric acid, and succinate acid. To achieve statistical power of 0.80, with a conservative correlation of 0.5 between repeated outcomes, the estimated sample size required was $N=12$. To account for an 18% dropout/disqualification rate and for equal groups we propose to enroll 14 adults with T1D, with an equal sample of men ($n=7$) and women ($n=7$).

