5.2 Statistical Methods

For aim 1, changes in the first principal component, as well as any additional components for which the associated eigenvalue is greater than one, will be evaluated using paired t-tests at the 2-sided 0.05 level. Changes in individual metabolic intermediates will be evaluated using paired t-tests at the 2-sided 0.01 level. Differences in metabolomics and counterregulatory hormones markers between treatment regimens will be evaluated using two-way ANOVAs [regimen (HIIT vs. MICT vs. CON) \times time (base vs. immediate post vs. 1h post)]. Exploratory analysis of the modulatory effects of sex on metabolomics markers will be evaluated using separate regimen-by-sex mixed factorial ANOVAs [regimen \times sex], at each time point.

For aim 2, CGM data will be evaluated as previously recommended; data will be aggregated over the 24hrs; area under the curve data will be compared across trials.(25) Counter-regulatory hormones will be evaluated using a two-way mixed factorial ANOVA. Activity data will be captured to potentially be used as a covariate when collating CGM data.

For aim 3, spearman correlations will be completed to understand associations between metabolomics outcomes and physiological variables (i.e. body fat, lean mass, visceral fat).

6 Safety and Adverse Events

Risks associated with participating in this study are **possible**. In-test monitoring by the research team, who are certified fitness professionals trained in CPR/AED, are in place to ensure the safety of all subjects. Personnel trained in phlebotomy and with radiation exposure training will complete the blood draws and DXA scans, respectively.

In accordance with the Exercise and Sport Science Institutional Review Board Standard Operating Procedures (EXSS-IRB SOP), 3 trained research personnel (for safety purposes per IRB procedures) will perform cardiorespiratory fitness testing. Other precautions include: licensed medical professional (MD, ATC) on call, operational AED, and a land line within 10 feet of the testing in order to make emergency call, if required. Additionally, the lab is located within 500 feet of the University Athletic Training facility. If a cardiovascular event does occur, 911 will be called; UNC Hospitals and Emergency room are in very close proximity to the lab.

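### Fourteen subjects cannot be split equally over the orders of three conditions, and no analysis includes visit order, so drift across visits is neither fully balanced nor modelled

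*Combined protocol and SAP*

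**What the plan says.** Section 3.1 describes a cross-over in which subjects "will undergo three conditions, in a randomized order". Section 3.3 fixes the number: "Fourteen patients (7 females, 7 males) with T1D, for at least one year, will be enrolled for this study". On allocation, section 3.7 says that the PI uses random allocation software and adds: "The allocation sequence will be generated with equal treatment sequence order". It names no set of sequences, block size or stratification.

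Section 5.1 says "the estimated sample size required was $N=12" and raises this to 14 for dropout. Section 3.6 lists reasons for withdrawal and is silent on replacement.

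The between-regimen analyses in section 5.2 are "two-way ANOVAs [regimen (HIIT vs. MICT vs. CON) \times time (base vs. immediate post vs. 1h post" (time here is within a visit), regimen by sex ANOVAs at each time point, and a comparison of CGM area under the curve across trials. Section 5.2 also has paired t-tests on changes. None contains period, sequence or visit order. Section 4.1 sets at least seven days between exercise trials, which bears on carryover rather than on drift over visits.

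**The concern.** A three-period cross-over has two usual protections against drift over visits, such as habituation to the laboratory, the fasting and the blood draws. One is to balance the orders, so that each regimen falls equally often on each visit. The other is to put visit order in the model. The plan relies on the first, which cannot be met exactly with 14 subjects, and it omits the second.

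Two things follow. The realised regimen means carry some of any drift. Drift left in the residual also makes standard errors larger than they need be, even where the orders happen to be balanced. In a 14-person study, the lost precision is the more important of the two.

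**Working it through.** **Inputs.** N = 14, 7 per sex (3.1, 3.3); three conditions (3.1); 12 evaluable, 18% loss and correlation 0.5 (5.1). Drift per visit, δ, is not in the documents, so imbalance is given as a multiple of δ, and error rates for a range of assumed values.

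**The plan's enrolment figure.** 12 / (1 − 0.18) = 14.6, which rounds up to 15; the stated 14 gives 14 × 0.82 = 11.5 expected completers. The difference is small and is not the point here. It does show that about two losses are planned for.

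**Divisibility.** 14/6 = 2.33 and 14/3 = 4.67, so equal counts are impossible. The 12 evaluable would divide: 12/6 = 2 and 12/3 = 4.

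**Imbalance at N = 14.** Under linear drift, the unadjusted HIIT-MICT difference carries δ times the mean of (HIIT visit position − MICT visit position).

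| Order | Position difference |
|---|---|
| HIIT, MICT, CON | −1 |
| HIIT, CON, MICT | −2 |
| MICT, HIIT, CON | +1 |
| MICT, CON, HIIT | +2 |
| CON, HIIT, MICT | −1 |
| CON, MICT, HIIT | +1 |

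The six sum to zero, so two complete blocks contribute nothing and only the two surplus subjects count. The worst surplus pair is 2 + 1 = 3, giving 3/14 = 0.21. Over the 15 possible pairs, the absolute sums total 20, so the mean is 20/15/14 = 0.10. In 3 of the 15 (mirror-image orders), the imbalance is zero for all three contrasts.

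**After two losses.** To leave two per order, one subject must be lost from each of the two orders that hold three: 3 × 3 / 91 = 9.9%, where 91 is the number of ways to lose 2 of 14. Simulation of random losses gives a mean absolute imbalance of 0.16 and a 95th percentile of 0.42. The worst case is (3 + 4)/12 = 0.58.

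**Size against the standard error.** With unit SD and correlation 0.5, a HIIT-MICT difference has variance 2(1 − 0.5) = 1, so its standard error at N = 12 is 1/√12 = 0.29 SD. At an assumed δ of 0.5 SD, the 95th-percentile imbalance is 0.42 × 0.5 = 0.21 SD, which is less than one standard error.

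**Effect on the test.** Over the six orders, the mean squared position difference is (1+4+1+4+1+1)/6 = 2, so unmodelled drift raises the variance of a paired difference from 1 to about 1 + 2δ². With near-balanced orders, the estimate itself does not vary correspondingly more. The paired test (13 df, critical value 2.16) is therefore conservative:

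| Assumed δ (SD per visit) | SE inflation √(1+2δ²) | Approximate true level of a 5% test |
|---|---|---|
| 0 | 1.00 | 5% |
| 0.25 | 1.06 | 4% |
| 0.5 | 1.22 | 2% |
| 1.0 | 1.73 | 0.2% |

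Simulation at δ = 0.5 agrees: about 2% with no losses and slightly more with two. A model with subject and period restores about 5%. The paired test stands in for the planned ANOVAs.

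**Where it applies.** HIIT and MICT each have a same-visit baseline draw, so an additive visit shift cancels in their regimen by time interaction. It does not cancel for CON blood outcomes (section 4.1 gives CON a single draw), for comparisons at one time point such as regimen by sex, or for CGM area under the curve.

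**Cost of a period term.** With two blocks of six plus two different extra orders, the period-adjusted HIIT-MICT contrast keeps 98.5% to 100% efficiency and uses 2 error df.

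**The case against.** The strongest reply is that randomising the order already protects the comparison. That stands: the expected imbalance is zero and false positives are not inflated. A reader might infer that the regimen comparisons are biased, but the documents do not support this. What remains is chance imbalance in one realised allocation, and lost precision.

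Second, section 3.7 may describe how the list is generated rather than promise equal counts. That is a fair reading. If it means simple randomisation with equal chances, however, the imbalance is larger (mean 0.30, 95th percentile 0.71 of a visit's drift), and a period term is still missing. If it means only HIIT before MICT or the reverse, 7/7 is possible, but CON is then not balanced over the three visits.

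Third, a VO2peak test, laboratory familiarisation and a home practice session precede the trial visits (section 4.1), so drift may be small. This also stands, and it is why no single drift value is relied on.

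Three further inferences should be avoided:

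- That withdrawals will not be replaced within sequence. The documents give no replacement rule either way.
- That 7 per sex makes the allocation worse. That requires stratification by sex, which is not stated.
- That "for equal groups we propose to enroll 14 adults with T1D" refers to sequence groups. The sentence goes on to equal numbers of men and women.

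**Conclusion.** The point holds in a limited form. Exact equality of sequences is impossible with 14 subjects and three conditions, and no planned analysis models visit order. The chance imbalance is modest, and the more dependable cost is an inflated error term. At an assumed drift of 0.5 SD per visit, the standard error of a paired contrast is about 22% larger than it need be; if drift is near zero, almost nothing is lost.

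The figures assume linear drift, near-equal allocation over six orders, losses unrelated to order and, for the test level, a correlation of 0.5. Severity is minor to moderate: the harm is limited, but the correction is nearly free.

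**What to change.** 1. In section 5.2, add period (visit order) as a fixed factor, with subject as a random or blocking factor, to the regimen comparisons for metabolites, hormones and CGM area under the curve. Use all completed sessions, including those of subjects who miss a visit.
2. In section 3.7, replace the statement of equal sequence order with allocation as near equal as possible over the six orders: two complete blocks of six, plus a randomly chosen mirror-image pair of orders for the other two subjects. The mirror pair removes linear drift from every contrast at N = 14; the period term covers other shapes and the imbalance left by losses.

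Replacing dropouts within their own order is not a substitute. Balance fails again after a late withdrawal, and the replacement's order would be predictable to the PI, who assigns it.

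The cost is a revised allocation list, one model factor, two error degrees of freedom and at most about 1.5% efficiency at N = 14. Enrolment does not change.
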